## 5.6 SAFETY MONITORING

Adverse and severe adverse events, including social harms such as violence or breach of confidentiality, will be monitored, and unblinded results will be reviewed by the DSMB. The DSMB will make recommendations regarding any imbalances in safety outcomes.

**Table 5.3 Adverse and severe adverse events: shell table**

SAE #	PTIDNO	SAE description	Severity (Grade)	Onset date	Duration (days / unresolved)	Onset since randomization (days)	Relatedness to study

## 6. MODIFICATIONS TO ANALYSIS PLAN

Table 6.1 records modifications made to the analysis plan, and their justification.

**Table 6.1. Summary of modifications**

Description of modification	Date of modification	Modified SAP version	Original approach	Updated approach	Justification
Addition of secondary analysis with imputation of missing data (see section 5.5)	27 May 2018	3.0	None specified	A secondary analysis will be performed using multiple imputation by MCMC to impute VL 6 months after the time of last measurement.	Upon further thought, the study team realized that VL data were likely to be missing not at random and an imputed analysis could provide a less biased effect estimate.
Analytical approach for virologic failure primary outcome (see section 5.3)	1 May 2019	4.0	Incidence of virologic failure (HIV RNA $\geq 1000$ copies/mL) after the first 4 months post-enrollment will be compared between study arms using Cox proportional hazards regression.	We will stratify the study population by VL at enrollment, and conduct 2 separate survival analyses: 1. Incidence of virologic suppression among participants with unsuppressed VL at enrollment. 2. Incidence of virologic failure among participants with suppressed VL at enrollment.	Our study population is composed of two distinct groups: those entering the study on established suppressive therapy, and those not on suppressive therapy. The study team realized that the intervention may have distinct mechanisms of action for each group. We will therefore analyze them separately.
Addition of pre-specified secondary analysis of virologic failure (see section 5.7)	1 May 2019	4.0	None specified	Among participants who are virally suppressed at 6 months postpartum, incidence of virologic failure (HIV RNA $\geq 1000$ copies/mL) will be compared between study arms using Cox proportional hazards regression	This analysis will evaluate effects of SMS on longer term viral failure after the early postpartum period.

Addition of VL cutoff for virologic failure outcome (see section 5.3)	26 May 2020	5.0	Virologic failure = HIV RNA $\geq$ 1000 copies/mL	Virologic non-suppression = HIV RNA $\geq$ 1000 (primary) and $\geq$ assay limit of detection (secondary)	Since the study was originally funded, it is understood that levels below 1000 c/ml may be associated with transmission, so there is interest in additional analysis of lower cutoffs.
Modification of VL analysis approach	26 May 2020	5.0	We will stratify the study population by VL at enrollment, and conduct 2 separate survival analyses: 1. Incidence of virologic suppression among participants with unsuppressed VL at enrollment. 2. Incidence of virologic failure among participants with suppressed VL at enrollment.	Risk of virologic non-suppression will be analyzed as a repeated measure by GEE with Poisson link.  Previously specified analyses of incidence of virologic suppression and virologic failure will be performed as exploratory analyses.	The stratified analysis did not use all available data, or allow us to probe changes in the intervention's effect over time. In order to maximize power and allow estimation of effect modification by peripartum timepoint, we will treat virologic non-suppression as a repeated measure.
Removal of secondary analysis with imputation of missing VL data	26 May 2020	5.0	A secondary analysis will be performed using multiple imputation by MCMC to impute VL 6 months after the time of last measurement.	No imputation will be performed.	Our dataset has 10% missing data at 24 months postpartum but >40% missing data at 18 months postpartum. Imputation of the one final VL measure would not address the problem of missing VL for a repeated measures analysis, since the bulk of missingness is at intervening timepoints. Imputation of intermediate VL given such high levels of missingness is not advisable.

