### Specific Aims:

**AIM 1:** To compare mother-infant pairs receiving systematic, tailored unidirectional SMS messaging vs. bidirectional SMS dialogue vs. control (no SMS) for outcomes measured during 2-year postpartum follow-up, including:

- a) Maternal retention in care, ART refills, virologic non-suppression, and ART drug resistance
- b) Infant HIV infection and HIV-free survival
- c) Maternal perceptions of acceptability, utility and strengths/weaknesses of unidirectional and bidirectional SMS

*Hypothesis 1: Long-term retention, ART adherence, and maternal/infant outcomes will be enhanced by SMS. Mothers will endorse SMS approaches, preferring bidirectional messaging dialogue.*

**AIM 2:** To determine correlates of maternal treatment failure (loss to follow-up, virologic non-suppression, or ART resistance) and correlates of infant HIV infection in the cohort overall and stratified by arm, and characterize SMS interactions among women in the bidirectional SMS arm, including frequency of and changes in interactivity over time, relationship to pivotal time-points (delivery, cessation of breastfeeding, transfer of care to ART clinic), characteristics of high and low ‘interactors’, and topics motivating interactions.

*Hypothesis 2: Lack of disclosure to partner, distance to clinic, and poor understanding of need for lifelong ART, will be associated with maternal treatment failure. Interaction frequency with bidirectional SMS will decline over time, and ‘higher-interactors’ will be younger, primigravida, and more educated.*

**AIM 3:** To assess the cost-effectiveness of unidirectional SMS and bidirectional SMS interactions: a) Estimate net cost savings realized through the reduction of treatment failure and drug resistance. b) Estimate incremental cost-effectiveness in improving infant and maternal health outcomes.

*Hypothesis 3: Both interventions will be cost saving and cost-effective; bidirectional SMS will be more cost-effective.*

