### 3. SAMPLE SIZE CONSIDERATIONS

#### a. Analyses based on comparison of proportions

Assuming alpha=5%, power=80%, 2-sided test, 1:1:1 allocation ratio, with a sample size of 275 per arm, we would have sufficient power to detect an increase in retention or increase in virologic suppression (inverse of virologic failure) from 75% (control) to  $\geq 85\%$ , allowing for 10% attrition; we will also be able to detect an increase in ARV adherence from 85% to  $\geq 95\%$  (Table 6). Thus, the total cohort sample is 825 women. We could see a difference from 75% to 85% between control and unidirectional SMS and additionally detect a difference between uni- and bidirectional SMS (85% to 95%). Similarly, we will have sufficient power to detect an increase in infant HIV-free survival from 85% to  $\geq 95\%$ .

*Sample size for unidirectional or bidirectional SMS vs. control or unidirectional vs. bidirectional; gray shading shows cells with sufficient power and n is number per arm*

Intervention	Prevalence of outcome	Control			
		70%	75%	80%	85%
	85%	120	250	906	-
	90%	62	100	199	686
	95%	35	49	75	140

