### 4. USE OF INTENTION-TO-TREAT AND PER-PROTOCOL ANALYSES

Analysis of primary outcomes will be by intention to treat (all participants).

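### The added analysis of longer-term virologic failure selects women on suppression at 6 months postpartum, which SMS is meant to change, so it is not a randomised comparison; its status in the current SAP is also unclear

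*SAP*

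**What the plan says.** The analysis appears in one place, the version 4.0 row of SAP Table 6.1 dated 1 May 2019. "Among participants who are virally suppressed at 6 months postpartum, incidence of virologic failure" is to be compared between arms by Cox regression. The justification reads: "This analysis will evaluate effects of SMS on longer term viral failure after the early postpartum period". The row points to a section 5.7.

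The version 5.0 row on the VL analysis (26 May 2020) says: "Previously specified analyses of incidence of virologic suppression and virologic failure will be performed as exploratory analyses". Its cell for the original approach lists only the two analyses stratified by VL at enrolment, so it is not certain that the sentence covers the 6-month analysis. No row removes that analysis, whereas the withdrawal of multiple imputation has a row of its own.

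In the current SAP, section 5 ends at 5.6. Neither section 5.3 nor the results shell in Table 5.2 includes the 6-month analysis.

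Suppression is something the intervention is expected to change. Hypothesis 1 states "Long-term retention, ART adherence, and maternal/infant outcomes will be enhanced by SMS", and non-suppression is the first primary endpoint in SAP section 2. Section 3a plans for an "increase in virologic suppression (inverse of virologic failure) from 75% (control) to" 85% or more.

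**The concern.** A woman enters this risk set only if she is suppressed about 6 months after delivery, and longer than that after randomisation. If SMS improves early suppression, the SMS risk set includes women who would have been unsuppressed, and so left out, under control. The arms then differ in the kind of woman compared, and the hazard ratio mixes any later effect of SMS with that difference in make-up. The stated purpose is an effect of SMS; the method does not isolate one.

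At stake is the reading of durability. Protocol section 13 explains that long follow-up was chosen over a larger cohort because long-term outcomes matter most to programmes. A hazard ratio near or above 1 in this subset could be read as a benefit that has worn off when it reflects selection alone. If the selection runs the other way, a benefit could appear that is not there.

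**Working it through.** **Inputs from the SAP.** 275 per arm, two-sided 5%, 80% power, 10% attrition, suppression 75% v 85% (section 3a); HR 0.65 at 25 per 100 person-years in control (section 3b).

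**Assumptions not in the documents.** (a) The 75% v 85% difference is present at the 6-month visit. (b) SMS stops no woman from being suppressed. (c) Women suppressed only because of SMS later fail at k times the rate of women who would be suppressed in either arm. No document gives k, so a range is shown.

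**1. The plan's own figures.** For 75% v 85%, pooled formula without continuity correction: n = [1.96·√(2·0.80·0.20) + 0.842·√(0.75·0.25 + 0.85·0.15)]² / 0.10² = 250 per arm, as stated. For HR 0.65 at 25 per 100 person-years, Freedman's formula gives 175 events; over 2 years with linear person-time and division by 0.9 this is 235 per arm, against 238 stated. The design inputs are sound for use here.

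**2. Who enters the subset.** After attrition, 275 × 0.9 = 247.5 per arm. Control: 247.5 × 0.75 = about 186. SMS: 247.5 × 0.85 = about 210. Under (b) the SMS women are 75 parts suppressed in either arm and 10 parts suppressed only through SMS, so 10/85 = 12% of the SMS risk set has no control counterpart.

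**3. Apparent hazard ratio.** Apparent HR = true later HR × [p_c + (p_s − p_c)·k] / p_s, with p_c = 0.75 and p_s = 0.85. This is a ratio of average rates and ignores the gradual depletion of higher-risk women.

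| k | No later effect (true HR 1) | True later HR 0.65 |
|---|---|---|
| 0.5 | 80/85 = 0.94 | 0.61 |
| 1 | 85/85 = 1.00 | 0.65 |
| 1.5 | 90/85 = 1.06 | 0.69 |
| 2 | 95/85 = 1.12 | 0.73 |
| 3 | 105/85 = 1.24 | 0.80 |

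**4. Dependence on the early effect.** With suppression of 75% in both arms, the ratio is unbiased for every k. With 75% v 80% and no later effect, it is (75 + 5·2)/80 = 1.06 at k = 2.

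**5. Simulation check.** One underlying risk per woman drove both 6-month suppression and later failure, and SMS had no later effect. The rate ratio in the suppressed subset was 1.12 when SMS helped all women alike, 1.26 when it helped high-risk women more, 0.94 when it helped mainly low-risk women, and 1.00 when it did not change suppression. In all randomised women it was 1.00 in each case.

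**6. Missing VL.** The SAP does not say how a woman without a 6-month VL is classified. Table 6.1 reports 10% missing at 24 months and more than 40% at 18 months, but gives no figure for 6 months. This is a second selection, of unknown direction.

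**The case against.** The strongest reply is that the row is part of a change log and not of the operative plan: section 5.7 does not exist, and section 5.3 and Table 5.2 omit the analysis. This stands as far as status goes. A mismatch between a log and the current text is not itself a fault, and a reader should not infer that this is a standing confirmatory analysis. However, the point concerns the row's updated approach, which no later row withdraws, and version 5.0 says that previously specified failure-incidence analyses will be performed. The analysis could still be reported under a pre-specified label.

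A reader might infer that the hazard ratio is necessarily biased against SMS. The documents do not support that. The direction depends on k, and the bias vanishes at k = 1 or if SMS leaves 6-month suppression unchanged. What favours k above 1 is Hypothesis 2, which links treatment failure to non-disclosure, distance and poor understanding of lifelong ART. Such barriers may well outlast the first 6 months, but that is an argument and not a figure.

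A reader might also infer that the plan has no other view of long-term effect. It has. Section 5.3 compares cumulative incidence of non-suppression by 365 and 730 days postpartum without selecting on the 6-month VL, and version 5.0 justifies the repeated-measures GEE partly by effect modification over peripartum time.

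Nor should the attenuation be turned into a claim of lost power. No power is stated for this analysis, and the 25 per 100 person-years is set for the control arm, not for women already suppressed. There is also no conflict with SAP section 4, which requires intention to treat for primary outcomes only.

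**Conclusion.** The concern holds in a limited form. A comparison of arms among women suppressed at 6 months postpartum is not protected by randomisation and cannot be read as an effect of SMS on later failure, whatever k is. If the planned 10-point gain is present at 6 months and SMS prevents no suppression, 12% of the SMS risk set is unmatched. The apparent HR under no later effect then runs from 0.94 to 1.24 for k from 0.5 to 3. Bias against SMS is the likelier direction but is not established.

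The primary virologic analysis uses all available VL after enrolment and from 4 months after ART start, whatever the 6-month result, and is unaffected. What needs correcting is a secondary or exploratory analysis of unclear status whose stated purpose its method cannot meet.

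**What to change.** - **State the status.** Say whether the version 4.0 analysis is withdrawn or kept as exploratory, and resolve the reference to section 5.7.
- **Move the longer-term question to all randomised women.** Either add an arm-by-period term to the primary GEE, or compare arms for VL ≥1000 copies/mL after 6 and up to 24 months postpartum, whatever the 6-month VL was.
- **If failure from suppression is of interest,** use women suppressed at enrolment. That is a baseline condition, specified in version 4.0 and retained as exploratory in version 5.0.
- **If the 6-month subset is kept,** label it exploratory and non-randomised, do not interpret it as an effect of SMS, and say how a missing 6-month VL is handled.

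The cost is SAP wording and one re-specified model on data already collected. The small downside is that the all-women version mixes persistent with new viraemia: it gives the overall effect on later non-suppression, not the effect on new failure alone.
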